10.4.1 Study recording period and follow-up for adverse events and serious adverse events

If a patient discontinues from treatment and continues to have tumor assessments, drug or procedure-related SAEs must be captured until the patient is considered to have confirmed PD and will have no further tumor assessments.

The investigator is responsible for following all SAEs until resolution, until the patient returns to baseline status, or until the condition has stabilized with the expectation that it will remain chronic, even if this extends beyond study participation.

10.4.2 Causality collection

The Investigator will assess causal relationship between the IPs and each AE and answer “yes” or “no” to the question “Do you consider that there is a reasonable possibility that the event may have been caused by the investigational product?”

For SAEs causal relationship will also be assessed for other medication and study procedures. Note that for SAEs that could be associated with any study procedure, the causal relationship is implied as “yes.”

A guide to the interpretation of the causality question is found in **Error! Reference source not found..**

10.4.3 Relationship to protocol procedures

The Investigator is also required to provide an assessment of the relationship of SAEs to protocol procedures on the SAE report form. This includes both non-treatment-emergent (i.e., SAEs that occur prior to the administration of IP) and treatment-emergent SAEs. A protocol-related SAE may occur as a result of a procedure or intervention required during the study (e.g., blood collection). The following guidelines should be used by Investigators to assess the relationship of SAEs to the protocol:

- Protocol related: The event occurred due to a procedure or intervention that was described in the protocol for which there is no alternative etiology present in the patient’s medical record.
- Not protocol related: The event is related to an etiology other than the procedure or intervention that was described in the protocol. The alternative etiology must be documented in the study patient’s medical record.

10.4.4 Adverse events based on signs and symptoms

All AEs spontaneously reported by the patient or reported in response to the open question from the study personnel: “Have you had any health problems since the previous visit/you were last asked?” or revealed by observation will be collected and recorded in the CRF.

When collecting AEs, the recording of diagnoses is preferred, when possible, to recording a list of signs and symptoms. However, if a diagnosis is known and there are other signs or symptoms that are not generally part of the diagnosis, the diagnosis and each sign or symptom will be recorded separately.

10.4.5 Adverse events based on examinations and tests

The results from protocol-mandated laboratory tests and vital signs measurements will be summarized in the CSR. Deterioration as compared to baseline in protocol-mandated laboratory values and vital signs should therefore only be reported as AEs if they fulfill any of the SAE criteria or are the reason for discontinuation of treatment with the IPs.

Clinical Study Protocol

Investigational Drug Substance: MEDI4736 Sirolimus (Rapamune)

Study Number **19-20015**

Edition Number: 4

Date: **11 February 2022**

If deterioration in a laboratory value or vital sign is associated with clinical signs and symptoms, the sign or symptom will be reported as an AE and the associated laboratory result or vital sign will be considered as additional information. Whenever possible, the reporting Investigator should use the clinical rather than the laboratory term (e.g., anemia versus low hemoglobin value). In the absence of clinical signs or symptoms, clinically relevant deteriorations in non-mandated parameters should be reported as AEs.

Deterioration of a laboratory value that is unequivocally due to disease progression should not be reported as an AE/SAE.

Any new or aggravated clinically relevant abnormal medical finding at a physical examination as compared with the baseline assessment will be reported as an AE.

10.4.6 Hy's Law

Cases where a patient shows elevations in liver biochemistry may require further evaluation and occurrences of AST or ALT $\geq 3 \times$ ULN together with total bilirubin $\geq 2 \times$ ULN may need to be reported as SAEs. Please refer to **Error! Reference source not found.** for further instruction on cases of increases in liver biochemistry and evaluation of Hy's law.

10.4.7 Disease progression

Disease progression can be considered as a worsening of a patient's condition attributable to the disease for which the IP is being studied. It may be an increase in the severity of the disease under study and/or increases in the symptoms of the disease. The development of new or progression of existing metastasis to the primary cancer under study should be considered as disease progression and not an AE. Events that are unequivocally due to disease progression should not be reported as an AE during the study.

10.4.8 New cancers

The development of a new cancer should be regarded as an SAE. New primary cancers are those that are not the primary reason for the administration of the IP and have been identified after the patient's inclusion in this study.

10.4.9 Deaths

All deaths that occur during the study treatment period, or within the protocol-defined follow-up period after the administration of the last dose of study drug, must be reported as follows:

- Death clearly resulting from disease progression should be reported to the Study Monitor/Physician at the next monitoring visit and should be documented in the CRF in the Statement of Death page. It should not be reported as an SAE.

- Where death is not due (or not clearly due) to progression of the disease under study, the AE causing the death must be reported to the Study Monitor/Physician as an SAE within 24 hours. It should also be documented in the Statement of Death page in the CRF.
- The report should contain a comment regarding the co involvement of PD, if appropriate, and should assign main and contributory causes of death.
- Deaths with an unknown cause should always be reported as an SAE. It should also be documented in the Statement of Death page in the CRF.
- A post mortem may be helpful in the assessment of the cause of death, and if performed, a copy of the post-mortem results should be forwarded to AstraZeneca Patient Safety or its representative.

Deaths occurring after the protocol defined safety follow up period after the administration of the last dose of study drug should be documented in the Statement of Death page. If the death occurred as a result of an event that started after the defined safety follow up period and the event is considered to be due to a late onset toxicity to study drug, then it should also be reported as an SAE.

AstraZeneca/MedImmune retains the right to request additional information for any patient with ongoing AE(s)/SAE(s) at the end of the study, if judged necessary.

10.4.10 Follow-up of unresolved adverse events

Any AEs that are unresolved at the patient's last visit in the study are followed up by the investigator for as long as medically indicated, but without further recording in the CRF.

AstraZeneca/MedImmune retains the right to request additional information for any patient with ongoing AE(s)/SAE(s) at the end of the study, if judged necessary.

10.4.11 Post-study events

After the patient has been permanently withdrawn from the study, there is no obligation for the investigator to actively report information on new AE or SAEs occurring in former study patients after the 90-day safety follow-up period for patients treated with durvalumab. However, if an investigator learns of any SAEs, including death, at any time after the patient has been permanently withdrawn from study, and he/she considers there is a reasonable possibility that the event is related to study treatment, the investigator should notify the study sponsor and AstraZeneca/MedImmune Patient Safety.

Clinical Study Protocol

Investigational Drug Substance: MEDI4736 Sirolimus (Rapamune)

Study Number **19-20015**

Edition Number: **4**

Date: **11 February 2022**

10.5 Reporting of serious adverse events

All SAEs will be reported, whether or not considered causally related to the investigational product, or to the study procedure(s). The reporting period for SAEs is the period immediately following the time that written informed consent is obtained through 90 days after the last dose of durvalumab or until the initiation of alternative anticancer therapy. The investigator and/or Sponsor are responsible for informing the Ethics Committee and/or the Regulatory Authority of the SAE as per local requirements.

All serious, related and unexpected adverse events must be reported to AstraZeneca regardless of the country where the study is conducted.

For those events requiring expedited reporting to the regulatory authorities, the investigator and/or sponsor must inform all applicable regulatory authorities (e.g. FDA), via a MedWatch/AdEERs or applicable required regulatory form (e.g. CIOMS), of any serious, related and unexpected adverse events in accordance with reporting obligations (e.g. FDA21 CFR 312.32) and will concurrently forward all such reports to AstraZeneca in English. A copy of the MedWatch/AdEERs report must be emailed to AstraZeneca at the time the event is reported to the regulatory authorities (e.g. FDA). It is the responsibility of the sponsor to compile all necessary information and ensure that the regulatory authorities receive a report according with the applicable reporting requirement timelines and to ensure that these reports are also submitted to AstraZeneca at the same time.

* A *cover page* should accompany the **MedWatch/AdEERs** form indicating the following:

- “Notification from an Investigator Sponsored Study”
- The investigator IND number assigned by the FDA
- The investigator’s name and address
- The trial name/title and AstraZeneca ISS reference number (ESR-19-20015)

* Sponsor must also indicate, either in the SAE report or the cover page, the *causality* of events *in relation to all study medications* and if the SAE is *related to disease progression*, as determined by the principal investigator.

* ***Send SAE report and accompanying cover page by way of email to AstraZeneca’s designated mailbox:*** [contact]

If a non-serious AE becomes serious, this and other relevant follow-up information must also be provided to AstraZeneca and the FDA.

Clinical Study Protocol

Investigational Drug Substance: MEDI4736 Sirolimus (Rapamune)

Study Number **19-20015**

Edition Number: 4

Date: **11 February 2022**

Serious adverse events that do not require expedited reporting to the regulatory authorities still need to be reported to AstraZeneca using the MedDRA coding language for serious adverse events. This information should be reported on a monthly basis and under no circumstance less frequently than quarterly.

10.5.1 Reporting of deaths to AstraZeneca

All deaths must be recorded and reported as outlined in Section 10.5. In addition, all SAEs resulting in death or death of unknown cause must be reported to AstraZeneca via [contact] within 7 calendar days of awareness or sooner when required (See Section 10.5).

10.5.2 Other events requiring reporting

10.5.3 Overdose

An overdose is defined as a patient receiving a dose of durvalumab in excess of that specified in the Investigator's Brochure, unless otherwise specified in this protocol.

Any overdose of a study patient with durvalumab, with or without associated AEs/SAEs, is required to be reported within 24 hours of knowledge of the event to the sponsor. The sponsor must report these to AstraZeneca/MedImmune Patient Safety or designee using the designated Safety e-mailbox (see Section 10.5 for contact information) within 7 calendar days or sooner when required (see Section 10.5). If the overdose results in an AE, the AE must also be recorded as an AE (see Section 10.5). Overdose does not automatically make an AE serious, but if the consequences of the overdose are serious, for example death or hospitalization, the event is serious and must be recorded and reported as an SAE (see Section 10.5). There is currently no specific treatment in the event of an overdose of durvalumab.

An overdose of sirolimus is required to be reported within 24 hours of knowledge of the event to the sponsor.

The investigator will use clinical judgment to treat any overdose.

10.5.4 Hepatic function abnormality

Hepatic function abnormality that fulfills the biochemical criteria of a potential Hy's Law case in a study patient, with or without associated clinical manifestations, is required to be reported as "hepatic function abnormal" ***within 24 hours of knowledge of the event*** to the sponsor. The Sponsor must report these events to AstraZeneca Patient Safety using the designated Safety e-mailbox (see Section 10.5 for contact information) within 7 calendar days or sooner when required, unless a definitive underlying diagnosis for the abnormality (e.g., cholelithiasis or bile duct

obstruction) that is unrelated to investigational product has been confirmed. The criteria for a potential Hy's Law case is Aspartate Aminotransferase (AST) or Alanine Aminotransferase (ALT) ≥ 3 times Upper Limit of Normal (ULN) together with Total Bilirubin (TBL) ≥ 2 times ULN at any point during the study following the start of study medication irrespective of an increase in Alkaline Phosphatase (ALP).

- If the definitive underlying diagnosis for the abnormality has been established and is unrelated to investigational product, the decision to continue dosing of the study patient will be based on the clinical judgment of the investigator.
- If no definitive underlying diagnosis for the abnormality is established, dosing of the study patient must be interrupted immediately. Follow-up investigations and inquiries must be initiated by the investigational site without delay.

Each reported event of hepatic function abnormality will be followed by the investigator and evaluated by the sponsor and AstraZeneca/MedImmune.

10.5.5 Pregnancy

10.5.6 Maternal exposure

If a patient becomes pregnant during the course of the study, the IPs should be discontinued immediately.

Pregnancy itself is not regarded as an AE unless there is a suspicion that the IP under study may have interfered with the effectiveness of a contraceptive medication. Congenital abnormalities or birth defects and spontaneous miscarriages should be reported and handled as SAEs. Elective abortions without complications should not be handled as AEs. The outcome of all pregnancies (spontaneous miscarriage, elective termination, ectopic pregnancy, normal birth, or congenital abnormality) should be followed up and documented even if the patient was discontinued from the study.

If any pregnancy occurs in the course of the study, then the Investigator or other site personnel should inform the sponsor within 1 day, i.e., immediately, but **no later than 24 hours** of when he or she becomes aware of it.

The sponsor will work with the Investigator to ensure that all relevant information is provided within 1 to 5 calendar days. The Sponsor must report to AstraZeneca Patient Safety using the designated Safety e-mailbox (see Section 10.5 for contact information) within 7 calendar days or sooner when required (see Section 10.5), for pregnancies with SAEs and within 30 days for all other pregnancies.

Clinical Study Protocol

Investigational Drug Substance: MEDI4736 Sirolimus (Rapamune)

Study Number **19-20015**

Edition Number: **4**

Date: **11 February 2022**

The same timelines apply when outcome information is available.

10.5.7 Paternal exposure

Male patients should refrain from fathering a child or donating sperm during the study and for 180 days after the last dose of durvalumab + any drug combination therapy or 90 days after the last dose of durvalumab monotherapy, whichever is the longer time period.

Pregnancy of the patient's partner is not considered to be an AE. However, the outcome of all pregnancies (spontaneous miscarriage, elective termination, ectopic pregnancy, normal birth, or congenital abnormality) occurring from the date of the first dose until 180 days after the last dose of durvalumab + any drug combination therapy or 90 days after the last dose of durvalumab monotherapy, whichever is the longer time period should, if possible, be followed up and documented.

Where a report of pregnancy is received, prior to obtaining information about the pregnancy, the Investigator must obtain the consent of the patient's partner. Therefore, the local study team should adopt the generic ICF template in line with local procedures and submit it to the relevant Ethics Committees (ECs)/Institutional Review Boards (IRBs) prior to use.

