- Adequate normal organ and marrow function as defined in protocol
- Evidence of post-menopausal status or negative urinary or serum pregnancy test for female pre-menopausal patients.
- Measurable disease defined by RECIST v 1.1.
- Patient is able to take oral medications
- Patient consents to heavy water (D2O) self-administration, if enrolling in optional heavy water study
- Patient is willing and able to comply with the protocol for the duration of the study including undergoing treatment and scheduled visits and examinations including follow up.

Exclusion Criteria:

- Prior therapy for lung cancer including chemotherapy, hormonal therapy, or radiotherapy.
- Concurrent enrolment in another clinical study, unless it is observational
- Prior treatment with anti-PD-1, anti-PDL-1, including durvalumab other PD-1/PDL-1 pathway targeting agents, or mTOR inhibition.
- History of allogenic organ transplantation.
- Active or prior documented autoimmune or inflammatory disorders (including inflammatory bowel disease [e.g., colitis or Crohn's disease], systemic lupus erythematosus, Sarcoidosis syndrome, or Wegener syndrome [granulomatosis with polyangiitis, Graves' disease, rheumatoid arthritis, hypophysitis, uveitis, etc]). Exceptions listed in protocol below.
- Uncontrolled intercurrent illness
- History of another primary malignancy with exceptions noted in protocol
- QT interval corrected for heart rate using Fridericia's formula (QTcF) \geq 470 ms
- History of active primary immunodeficiency
- Active infection including tuberculosis, hepatitis B, hepatitis C
- Current or prior use of immunosuppressive medication within 14 days before the first dose of durvalumab. There are exceptions to this criterion listed below in the protocol
- Receipt of live attenuated vaccine within 30 days prior to the first dose of study medications

- Female patients who are pregnant or breastfeeding or male or female patients of reproductive potential who are not willing to employ effective birth control from screening to 90 days after the last dose of durvalumab
- Known allergy or hypersensitivity to any of the study drugs or excipients.
- Patients with a history of idiopathic pulmonary fibrosis, pneumonitis (including drug induced), organizing pneumonia, or evidence of active pneumonitis on screening chest CT scan

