10. Active infection including **tuberculosis** (clinical evaluation that includes clinical history, physical examination and radiographic findings, and TB testing in line with local practice), **hepatitis B** (known positive HBV surface antigen (HBsAg) result), **hepatitis C**. Patients with a past or resolved HBV infection (defined as the presence of hepatitis B core antibody [anti-HBc] and absence of HBsAg) are eligible. Patients positive for hepatitis C (HCV) antibody are eligible only if polymerase chain reaction is negative for HCV RNA.

11. Current or prior use of immunosuppressive medication within 14 days before the first dose of durvalumab. The following are exceptions to this criterion:

- a. Intranasal, inhaled, topical steroids, or local steroid injections (e.g., intra articular injection)
- b. Systemic corticosteroids at physiologic doses not to exceed 10 mg/day of prednisone or its equivalent
- c. Steroids as premedication for hypersensitivity reactions (e.g., CT scan premedication)

12. Receipt of live attenuated vaccine within 30 days prior to the first dose of IP. Note: Patients, if enrolled, should not receive live vaccine whilst receiving IP and up to 30 days after the last dose of IP.

13. Female patients who are pregnant or breastfeeding or male or female patients of reproductive potential who are not willing to employ effective birth control from screening to 90 days after the last dose of durvalumab monotherapy.

14. Known allergy or hypersensitivity to any of the study drugs or any of the study drug excipients.

Clinical Study Protocol

Investigational Drug Substance: MEDI4736 Sirolimus (Rapamune)

Study Number **19-20015**

Edition Number: 4

Date: **11 February 2022**

15. Prior randomisation or treatment in a previous durvalumab clinical study regardless of treatment arm assignment.
16. Patients with a history of idiopathic pulmonary fibrosis, pneumonitis (including drug induced), organizing pneumonia, or evidence of active pneumonitis on screening chest CT scan
17. Inability to stop prohibited concomitant medications listed in Section 7.7.2.
18. Judgment by the investigator that the patient is unsuitable to participate in the study and the patient is unlikely to comply with study procedures, restrictions and requirements.

Procedures for withdrawal of incorrectly enrolled patients are presented in Section 4.3

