7. RESTRICTIONS DURING THE STUDY AND CONCOMITANT TREATMENT(S)

7.1 Restrictions during the study

The following restrictions apply while the patient is receiving study treatment and for the specified times before and after:

Female patient of child-bearing potential

- Female patients of childbearing potential who are not abstinent and intend to be sexually active with a non-sterilized male partner must use at least 1 **highly** effective method of contraception (Table 3) from the time of screening throughout the total duration of the drug treatment and the drug washout period (90 days after the last dose of durvalumab monotherapy). Non-sterilised male partners of a female patient of childbearing potential must use male condom plus spermicide throughout this period. Cessation of birth control after this point should be discussed with a responsible physician. Periodic abstinence, the rhythm method, and the withdrawal method are not acceptable methods of birth control. Female patients should also refrain from breastfeeding throughout this period.

Male patients with a female partner of childbearing potential

- Non-sterilized male patients who are not abstinent and intend to be sexually active with a female partner of childbearing potential must use a male condom plus spermicide from the time of screening throughout the total duration of the drug treatment and the drug washout period (90 days after the last dose of durvalumab monotherapy). However, periodic abstinence, the rhythm method, and the withdrawal method are not acceptable methods of contraception. Male patients should refrain from sperm donation throughout this period.
- Female partners (of childbearing potential) of male patients must also use a highly effective method of contraception throughout this period (Table 3).

N.B Females of childbearing potential are defined as those who are not surgically sterile (ie, bilateral salpingectomy, bilateral oophorectomy, or complete hysterectomy) or post-menopausal.

Women will be considered post-menopausal if they have been amenorrheic for 12 months without an alternative medical cause. The following age-specific requirements apply:

- Women <50 years of age would be considered post-menopausal if they have been amenorrheic for 12 months or more following cessation of exogenous hormonal treatments and if they have luteinizing hormone and follicle-stimulating hormone levels in the post-menopausal range for the institution.

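### Men get two end dates for reproductive precautions: 90 days after durvalumab in Section 7.1, and 180 days in Section 10.5.7 for a combination, which is what the protocol calls this regimen

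*Combined protocol and SAP*

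**What the plan says.** Four places in the combined protocol and SAP set or test a period for male patients.

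- **Section 10.5.7, first paragraph:** "Male patients should refrain from fathering a child or donating sperm during the study and for 180 days after the last dose of durvalumab" given with any combination partner. A 90-day alternative is attached to durvalumab monotherapy, so that the period reads "180 days after the last dose of durvalumab + any drug combination therapy or 90 days after the last dose of durvalumab monotherapy", and the longer period governs.
- **Section 10.5.7, partner pregnancies:** outcomes are to be followed where possible for pregnancies "occurring from the date of the first dose until 180 days after the last dose of durvalumab + any drug combination therapy", with the same 90-day alternative and the same longer-period rule.
- **Section 7.1, male patients:** condom plus spermicide is required from screening through treatment and "the drug washout period (90 days after the last dose of durvalumab monotherapy"). Two further rules use that period: "Male patients should refrain from sperm donation throughout this period", and "Female partners (of childbearing potential) of male patients must also use a highly effective method of contraception throughout this period".
- **Section 4.2, exclusion 13, and the synopsis:** a man or woman of reproductive potential is excluded if unwilling to use birth control. Exclusion 13 sets the period "from screening to 90 days after the last dose of durvalumab monotherapy". The synopsis asks for "effective birth control from screening to 90 days after the last dose of durvalumab", without the word monotherapy.

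Every patient is planned to take sirolimus on days 1 to 21 and durvalumab from day 22 (Section 3.1 and Table 1).

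**The concern.** These are operating instructions to the same men, and they give different end dates. Sperm donation is the clearest case, because one act by one group has a 90-day limit in 7.1 and a 180-day limit in 10.5.7. Site staff who counsel from 7.1, the section on restrictions, would tell a man that his precautions end at 90 days. Staff who read 10.5.7 would tell him 180.

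Eligibility follows the shorter period. A man who is willing to comply for 90 days but no longer passes exclusion 13, yet 10.5.7 then asks him for 180. Partner-pregnancy follow-up also runs beyond the date on which 7.1 ends contraception.

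The matter at stake is reproductive-safety counselling. Sample size, error rates and the pathologic response analysis are untouched.

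**Working it through.** **Which branch of 10.5.7 applies.** The section gives one period for durvalumab with any combination partner and another for durvalumab alone.

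- The regimen is called a combination in Sections 1.5.1.2, 1.6.2, 2.2, 2.3 and 3.1. Section 1.6.2 adds that the risks of the combination are not known.
- No arm, cohort or planned schedule gives durvalumab without sirolimus.
- If both labels were thought to fit, 10.5.7 takes the longer period.

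On the protocol's own terms, 10.5.7 therefore gives 180 days.

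**Study days affected.** Input: the second and last durvalumab dose is nominally on day 43 (schedule of assessments).

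| Rule | Formula | Ends after |
|---|---|---|
| 7.1 | 43 + 90 | day 133 |
| 10.5.7, combination | 43 + 180 | day 223 |
| Difference | 223 − 133 | 90 days (study days 134 to 223) |

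The gap does not depend on the date of the last dose, since 180 − 90 = 90 in every case. The ±3-day visit window moves both ends together: 130 and 220 for a last dose on day 40, 136 and 226 for day 46.

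**How many men.** The accrual table plans 15 men among 30 patients. The sperm-donation rule addresses male patients generally. The number with a partner of childbearing potential is not given, so I make no count for the contraception rule.

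**Drug remaining at 90 days (context for the 90-day option).** Section 1.5.1.3 gives durvalumab a half-life of about 17 days, and 90 / 17 = 5.3 half-lives. Section 1.6.2.2 gives sirolimus a half-life of 72.3 hours in males. From the last sirolimus dose on day 21 to day 133 is 112 days, and 112 × 24 / 72.3 = 37 half-lives. Elimination alone does not settle reproductive risk, so these figures do not decide between the two periods.

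**The case against.** **Dosing is sequential, so the durvalumab phase might count as monotherapy.** This is the best counter-argument. Sirolimus stops on day 21 and durvalumab starts on day 22. The title, Section 3.4 and the statistical sections say that one drug follows the other. Sections 4.2, 6.4.1 and 7.1 use monotherapy wording for this study's patients, and adverse-event collection also stops 90 days after durvalumab. On that reading 10.5.7 would also give 90 days.

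It does not remove the problem. The protocol nowhere says that the durvalumab phase is to be treated as monotherapy. Exposures are expected to overlap: Section 8.2.3 schedules the sirolimus trough sample on the day of the first durvalumab dose (Section 8.1.2 says day 23). If monotherapy was meant, the 180-day branch applies to nobody and still needs editing. What stands is that leftover template text is a plausible source, since unfilled placeholders remain in Sections 10.2.3 and 10.4. The 180-day figure is therefore not evidence of a deliberate choice.

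**The rules can all be satisfied together.** This is true: a man who observes 180 days meets all four places. Section 10.5.7 is worded as advice to refrain, and 7.1 sets a minimum without authorising donation on day 91. Exclusion 13 and the synopsis test willingness at entry and are not release dates. The direct mismatch is between 7.1 and 10.5.7, and it is a mismatch of stated periods.

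**Stronger readings that a reader might infer.**

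- *That 90 days is unsafe.* Nothing in the documents shows that 180 days is medically needed, and the consent text was not available for review.
- *That 10.5.7 restricts men for years.* It also applies the restriction during the study, and Section 13.3 ends the study about 2 years after the last patient's last dose. If the restriction ran to that point, adding 180 days after the last dose would be redundant. The sentence itself points to the treatment period.
- *That existing follow-up contacts would cover the longer period.* Appendix 2 lists no contraception or partner-pregnancy check at the 3- and 6-month contacts, so this cannot be assumed.

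**Conclusion.** The inconsistency is real and should be corrected. Section 7.1 ends male precautions 90 days after the last durvalumab dose. Section 10.5.7, applied to a regimen that the protocol calls a combination, ends them at 180 days. The stated periods differ by 90 days, nominally study days 134 to 223, and exclusion 13 and the synopsis are aligned with the shorter one.

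The day numbers assume a last dose on day 43. The choice of the 180-day branch rests on the protocol's own description of the regimen and on 10.5.7's longer-period rule. Confidence is high for the mismatch in wording. The documents do not settle which period is medically right. The women's 90-day period is outside this point.

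**What to change.** State one male period in Section 7.1, exclusion 13, the synopsis and both paragraphs of 10.5.7, and delete the unused monotherapy and combination branches.

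- **Default:** 180 days after the last durvalumab dose, which is what 10.5.7's own rule gives.
- **Alternative:** if the sponsor documents that 90 days is adequate for this sequential regimen, change 10.5.7 to 90 days and leave the length in the other three places as it is.

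Exclusion 13 and the synopsis cover men and women in one sentence, so state the men's period separately there if it changes. As a wording clean-up only, have 10.5.7 refer to the study treatment period in place of the study as a whole.

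The cost is a wording amendment with matching patient-facing text. Under the default, men may carry the restriction for up to 90 days longer. The statistical plan does not change.
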